While few studies have evaluated psychosocial interventions for oncology nursing providers, it is hoped that participants will learn new skills that may reduce work-related stress and compassion fatigue.

POTENTIAL BENEFITS TO SOCIETY

The purpose of this study is to test an intervention to enhance skills among oncology nurses and support staff to cope with work-related stress. Rates of stress and emotional exhaustion are high among nurses with specialized training, and the extent to which quality on-site support and education programs are available to providers varies widely. Given the existing nursing shortage and the potential for work-related burnout, the development of an efficient, low-cost psychosocial training program for oncology nurses has the potential to reduce both patient and provider frustrations, to increase provider retention, and to enhance care provision.

18) Vulnerable Populations*

This study does not enroll any vulnerable populations. This study does not include any pregnant women, neonates, prisoners, children, or cognitively impaired adults.

19) Setting*

The training will take place at the University of Miami Sylvester Comprehensive Center.

20) Resources Available*

Principal Investigator, [name] is an Associate Professor of Psychiatry at the University of Miami Miller School of Medicine and Associate Director of Cancer Support Services at the Sylvester Comprehensive Cancer Center. [name] has been conducting research on oncology providers with the goal of improving patient care. He conducted a NIH-funded national survey on how oncologists manage psychosocial distress and is currently studying the relationships between oncologists' dispositional affect and the care that they deliver, also funded by NIH. [name] developed and tested psychological skills training interventions for oncology nurses that have decreased work-related stress and medical errors. [name] will oversee the research coordinator in the recruitment of participants and management of data.

[name], Associate Professor of Psychology and Director of Contemplative Neuroscience, Mindfulness Research & Practice Initiative, University of Miami. Her research focuses on the brain bases of attention, working memory, and mindfulness-based training. She has experience in the development of mindfulness treatment manuals for psychological distress. [name] will oversee the study personnel involved in the educational training and administration.

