 - Practice being present when someone else is in a difficult situation. Practice to "breathe it in" without having to immediately fix it, but rather recognizing that your willingness to "be with (breathe with)" the person and his/her suffering is an act of compassion.

Session Eight: Integrated Daily Compassion Cultivation Practice (2 hours)

- Opening practice: Settling the mind and intention-setting (approximately 10 minutes).
- Check-in about last week's home practice (approximately 10 minutes).
- Pedagogy and science: Brief summary of the topics covered in each of the previous classes. Discussion on how to integrate the different steps of the meditation practices and set up a daily practice (approximately 25 minutes).
- In-class practice: Integrated daily compassion cultivation practice and debrief (approximately 30 minutes).
- Group sharing: Participants are encouraged to reflect on their personal experience with the course and provide feedback (approximately 30 minutes).
- Closing: Home practice, reading/quote, and dedication practice (approximately 15 minutes).
- o Meditation Practice: Integrated daily compassion cultivation practice.
- o Informal Practices:
 - Reflect how you would like to continue practicing compassion in everyday life. Select your favorite informal practices and review your own intentions for choosing compassion.

Assessments

To protect the confidentiality of participants, all data will be collected using study ID numbers and assessments will be completed on-line with an e-mail link to the questionnaires in RedCap. Only the study PI and research coordinator will have access to the key that links code names to real names.

At baseline, all nurses will be asked to complete a demographic questionnaire with questions on age, sex, race/ethnicity, practice site, years of nursing experience, and type of nursing experience.

All nurses will complete the following assessments at baseline and post program (7-10 weeks).

Perceived Stress Scale (Cohen, et al., 1983; Cohen and Williamson, 1988): This 14-item instrument is the most widely used scale to measure the perception of stress. The items ask the frequency of different feelings of stress over the past 30 days.

Maslach Burn Out Inventory, Human Services version (Maslach, et al., 2009): This 22-item self-report instrument measures three areas of burn out: emotional exhaustion, depersonalization, and personal achievement. It is considered the standard for assessing burn out.

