Resistance to Sunk Cost	X	X	
Questionnaire on using skills in practice		X	X

The participants are anticipated to complete the study between 6-7 months.

10) Study Endpoints*

The primary outcome will be feasibility defined by at least 75% of the participants completing at least 75% of the program. The secondary outcome will be changes in Perceived Stress Scale from baseline to post-intervention. Other secondary outcomes will be tested on a preliminary basis: changes in target skill areas (e.g., coping self-efficacy, mindfulness, and distress tolerance), burn out, and health-related quality of life from baseline to post-intervention.

11) Data Storage*

We are collecting data on participant demographics (e.g., age, sex, race/ethnicity, work location, nursing experience) and the following instruments/questionnaires: Perceived Stress Scale, Maslach Burn Out Inventory, SF-36, Self-Efficacy Scale, Philadelphia Mindfulness Scale, Distress Tolerance Scale, Cognitive Failures Questionnaire, Mind Wandering Questionnaire, Resistance to Sunk Cost and Questionnaire on using skills in practice.

All participant information will remain confidential and stored on the study PI's and research coordinators computers and in REDCap. Identifiers such as name will only be used during the initial data retrieval process and can be destroyed once all data records have been obtained and data analysis completed. REDCap is a free, secure, HIPAA-compliant web-based application hosted by the University of Miami's Research Information Technology. The REDCap system offers easy data management with audit

trails, reports for monitoring and querying participant records, and an automated export mechanism to statistical packages (SPSS, SAS, Stata, R/S-Plus). The program will include 8 sessions and each session will be recorded. The recordings will be done with a digital video camera. Files will be immediately downloaded after each session and will be uploaded privately to [name] Youtube Account. The videos will be accessible only to the participants with whom we share a link with and are not searchable online. The files will be also backed up to a secured server to which only lab members have access. These files will also be backed up on to an external hard drive and stored in a locked cabinet. After the files are backed up, they will be permanently deleted from the camera memory cards.

12) Data Management*

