We will compare changes from baseline to 7-10 weeks in the Perceived Stress Scale between the participants who completed the educational program and participants on the waitlist with a paired t-test. If the two-sided p-value is $\leq .05$, our hypothesis that the program results in reduction of perceived stress will be supported.

Similarly, we will compare differences from baseline to 7-10 weeks in scores on the Self-Efficacy Scale; Maslach Burnout Inventory; the two components of the Philadelphia Mindfulness Scale (Present-Moment Awareness and Acceptance); the Distress Tolerance Scale; and the SF-36.

Power Analysis

Effect sizes for changes in psychological factors following a compassion-based educational intervention in oncology nurses have not been tested. The goal of this trial is to estimate effect sizes for a larger adequately-powered trial. The sample size is similar to other small feasibility studies of educational interventions in healthcare workers. We will conduct hypothesis testing to examine differences in our endpoints from pre- to post-intervention, to aid in planning a future trial.

14) Provisions to Monitor the Data to Ensure the Safety of Participants*

There will be no independent monitoring of the data outside of the study staff and the UM IRB.

To ensure the usability of self-report data, the research coordinator will review all assessment measures to ensure their completeness.

All participant data will be kept in a computer file that is password protected and changed whenever staff changes. Only study staff will have access to these data. A link between ID number and participant's name will be kept in a separate file, also password protected (with a different password), accessible only to the study PI and research coordinator.

We do not plan to employ a Data Safety Monitoring Board because potential risks to participants are minimal.

OUTCOMES MONITORING

Quality Assurance of Collected Data

Data collection will be conducted in the form of assessments completed on-line via e-mail and in some cases via mail. The research coordinator will also review all measures to ensure their completeness, and tracking forms will be developed to ensure that the assessments have occurred.

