All participant data will be kept in electronic files that are password protected and changed whenever staff changes. Only study staff will have access to the data. A link between ID number and participant's name will be kept in a separate file, also password protected (with a different password), accessible only to the study PI and research coordinator. The PI will work with the research coordinator to ensure that the data were accurately entered into the data storage system. For every new consent form, the PI (or designee) will review the form within one week of completion, and make an action plan to address any concerns that may arise. The research coordinator will present a quality control report to the PI on a bi-weekly basis.

Quality Plan for Monitoring Recruitment and Retention

The research coordinator will produce a weekly recruitment and retention report during the recruitment phase to be reviewed with the PI or designee. This report will yield important data in the event that changes to recruitment or retention procedures are required.

Protocol Integrity

Each individual educational session will be presented to the PI on a weekly basis, with a primary emphasis on what occurred during study sessions. The research coordinator will track the assessments to ensure that they are occurring at the appropriate times.

15) Withdrawal of Participants*

Participants will be informed that they have the right to discontinue participation at any time.

Participants may be withdrawn from the training at any time at the principal investigator's discretion due to:

- Non-compliance
- Clinical judgment of the investigator
- Worsening of clinical condition as reflected by 1) cognitive inability to complete assessments on 2 consecutive occasions 2) clear decline in psychosocial or behavioral functioning 3) safety concerns (aggression towards self or others) that, per clinician judgment, requires in-patient psychiatric care; 4) onset of new, severe psychiatric illness such as mania, psychosis, or severe depression.

If a participant decides to withdraw from the research, they will be thanked for their time and efforts. They will also be informed that their decision to withdraw from the study will in no way affect the medical treatment they receive at the University of Miami. Any data collected prior to withdrawal will be destroyed in compliance with IRB procedures.

Adverse events:

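### Section 13 limits the stress analysis to nurses who completed the program, although post scores are planned for all nurses; nurses who worsen can be left out, which may bias the result toward benefit

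*Combined protocol and SAP*

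**What the plan says.** Section 13 (Data Analysis Plan) gives the only stated analysis of the Perceived Stress Scale: changes from baseline to 7-10 weeks are to be compared "in the Perceived Stress Scale between the participants who completed the educational program" and a waitlist group, by a paired t-test. The decision rule opens "If the two-sided p-value is" and sets the cut-off at .05, at which point the hypothesis of reduced stress counts as supported. The next paragraph, linked by the word *Similarly*, covers the Self-Efficacy Scale, Maslach Burnout Inventory, Philadelphia Mindfulness Scale, Distress Tolerance Scale and SF-36. The section does not define completion, describe an analysis of all enrolled nurses, or give a method for missing data.

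Other sections carry no such limit:

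- Section 8 (Assessments): "All nurses will complete the following assessments at baseline and post program (7-10 weeks". The Perceived Stress Scale is first on the list that follows.
- Section 10 (Study Endpoints): "The secondary outcome will be changes in Perceived Stress Scale from baseline to post-intervention".

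Section 15 says "Participants may be withdrawn from the training at any time" at the investigator's discretion. One of the listed grounds, under worsening of clinical condition, is a "clear decline in psychosocial or behavioral functioning". After a sentence on participants who decide to leave the research, the section adds: "Any data collected prior to withdrawal will be destroyed in compliance with IRB procedures".

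**The concern.** Read literally, Section 13 collects post scores from nurses who did not complete the program and then leaves them out of the stress analysis. That is harmless if non-completion has nothing to do with how stress changed. Section 15 gives a reason to doubt it: a decline in psychosocial functioning, which is close to what the stress, burn-out and quality-of-life scales measure, can lead to withdrawal from the training. A nurse who gets worse may thus become a non-completer, and the mean change is then taken over a group partly selected for doing better.

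Two uses of the result are exposed. One is the significance rule for reduced stress. The other is the effect-size estimate, which the Power Analysis paragraph of Section 13 gives as the purpose of the trial, for planning a larger study.

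**Working it through.** **Comparing the sections.** Section 8 does restrict collection where that is intended: only the questionnaire on using skills is limited to nurses who completed at least 75% of the program. The stress scale has no such condition. Section 13 also counts drop-out before the post assessment separately from missed sessions, so a nurse can miss sessions, still give a post score, and be outside the completer group.

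**The plan's own figure.** There is none to reproduce. No effect size, SD or power is stated, and 25 is a ceiling (Section 6).

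**How many non-completers the plan tolerates.** Section 10 calls the program feasible if at least 75% of participants complete at least 75% of it. With 25 enrolled, 0.75 × 25 = 18.75, so 19 completers are needed (19/25 = 76%). That leaves up to 25 − 19 = 6 non-completers.

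**Illustration of size.** Inputs from the documents: n = 25, two-sided alpha 0.05, k = 1 to 6 non-completers. Assumptions:

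- Stress change X is normal with true mean 0 and SD 1; positive values mean worse.
- Each nurse has a latent decline score L = ρX + √(1 − ρ²)Z, with Z an independent standard normal. The k nurses with the highest L do not complete.
- The remaining 25 − k changes are tested with a single-group pre-post t-test, t = mean / (s / √(25 − k)), because no waitlist group is enrolled.

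Results from 100,000 simulated trials, shown as spurious reduction in SD units, then the chance of a significant reduction:

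| Left out | Analysed | ρ = 0 | ρ = 0.3 | ρ = 0.5 | ρ = 1 |
|---|---|---|---|---|---|
| 0 | 25 | none; 2.5% | none; 2.5% | none; 2.5% | none; 2.5% |
| 1 | 24 | none; 2.5% | 0.023; 3.2% | 0.040; 4.1% | 0.081; 7.0% |
| 3 | 22 | none; 2.5% | 0.064; 4.9% | 0.107; 7.8% | 0.215; 23.3% |
| 6 | 19 | none; 2.5% | 0.117; 7.4% | 0.196; 14.4% | 0.393; 57.1% |

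(*None* means within 0.001 SD, which is simulation noise.)

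**Check.** Under this model the bias is proportional to ρ, so the ρ = 0.5 column should be half the ρ = 1 column: 0.5 × 0.081 = 0.041, 0.5 × 0.215 = 0.108, 0.5 × 0.393 = 0.197. These agree with 0.040, 0.107 and 0.196 to within 0.001.

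**The case against.** **The completer phrase may be only a label.** It sits in a sentence that contrasts the trained group with a waitlist described nowhere else, using a test that does not compare two groups. The endpoint, the hypotheses and the Power Analysis paragraph carry no completer limit. This is fair: intent is not established. But the sentence is the only stated analysis, and followed as written it omits available scores. Correcting the waitlist and the test would not by itself remove the phrase.

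**A reader might infer that the plan removes every nurse who worsens, by rule.** The documents do not support that. Withdrawal is discretionary, and decline is one ground among several. Nothing ties a rise in the stress score to withdrawal, or withdrawal to exclusion from analysis. A nurse whose stress rises but who finishes stays in. Because completion is undefined, a nurse withdrawn after 6 of 8 sessions (0.75 × 8 = 6) might still count as a completer.

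**A reader might take the restriction on the other five instruments as certain.** It rests only on the word *Similarly*. It is the natural reading, not an explicit one.

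**The larger figures need many selected nurses.** The study is described as minimal risk, and recorded sessions allow make-up of missed ones. Nothing in the documents predicts six decline-related withdrawals; the one-nurse row may be nearer the mark. This stands, and is why the table starts at 1 and includes ρ = 0.

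**Not all non-completers will have scores.** Those who drop out before the post assessment give none, and data may be destroyed for those who leave the research. This also stands: the fix recovers only nurses who still answer the survey, and a sensitivity analysis for the rest is optional.

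**Conclusion.** The concern holds in limited form. The stress analysis is written for completers, in conflict with the data collection in Section 8 and the endpoint in Section 10. Section 15 makes exclusion related to the outcome possible, and the likely direction favours the program.

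At an assumed correlation of 0.5 the spurious reduction runs from 0.04 SD (one nurse left out) to 0.20 SD (six), and the chance of a falsely significant reduction from about 4% to 14%, against 2.5% when all are analysed. The SD, the correlation and the number left out are all assumptions, so these figures show a possible size and not a finding about this trial. If non-completion is unrelated to stress change there is no bias.

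A reader might go further and quote a loss of power for the later trial. The documents do not support a figure: they give no effect size, and a single-group pre-post change is not the treatment effect of a controlled trial.

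This should be fixed, but it is not critical. Stress change is a secondary outcome under an exploratory aim, and the primary outcome, feasibility, already counts non-completers.

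**What to change.** - **Section 13:** replace the completer group with all enrolled nurses who have a baseline and a post-program score, whatever number of sessions they attended. Say that this applies to the other instruments too. Report the completer result as supplementary only, with completion defined. This can be done in the same rewrite that resolves the waitlist and the paired test.
- **Section 15:** state that nurses withdrawn from the training, but not from the research, are still sent the post survey. Reconcile this with the sentence on destroying data, so that it applies only to withdrawal from the research. The grounds for withdrawal need no change for this purpose.

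The cost is a few sentences, since the assessments are already planned for all nurses. The estimated reduction in stress may come out slightly smaller.

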Potential participants will be recruited via flyers and staff meetings. Interested individuals will be invited to call the clinical research coordinator to discuss eligibility criteria. If they meet eligibility criteria, the research coordinator will discuss the informed consent form. For eligible and interested individuals, consent will be emailed via REDCap (Research Electronic Data Capture).

6) Number of Participants*

The overall study aims to enroll one cohort up to 25 participants in total.

7) Study-Wide Recruitment Methods*

This is not a multicenter study. All study-related recruitment will be at the Sylvester Comprehensive Cancer Center. Potential participants will be recruited via flyers and staff meetings. Interested individuals will be invited to contact the study team directly. A study team member will then screen for eligibility and initiate the process of informed consent. For interested and eligible individuals, consent will be obtained and the decision to join the study will be documented. A member of the study team will then perform consent procedures by presenting the individual with a detailed, consent form to be electronically signed following the explanations by the study team member.

8) Procedures Involved*

After eligibility is determined and electronically written consent is obtained, study procedures will continue as follows:

Upon enrollment of our target sample (up to 25 enrollees), all participants will receive an email link to complete an online baseline assessment in REDCap. This will ensure that all participants complete the assessment within the same approximate timeframe.

Light food and beverage will be provided at each educational session. The training sessions will take place in the University of Miami IRB-approved HIPPA-compliant location at the Sylvester Comprehensive Cancer Center. Training sessions with participants may be recorded or filmed for the purposes of missed-session make up (see #11 'Data Storage' bottom paragraph), training quality assurance, and practice materials. Participants will receive up to 16 nursing continuing education credits, one for each hour of the program that they attend. Additionally, as *compensation* for their time and effort, all participants will receive a \$15 gift card after completing the post assessment.

Program

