21) Confidentiality*

All participants will be assigned a unique study ID number. Identifying information will be stored separately from other study data in a password-protected, encrypted Excel file. All data will be stored on secure servers at the University of Miami. REDCap software will be utilized during the study to maximize data security. Only authorized study personnel will have access to identifying information throughout the course of the study.

22) Local Number of Participants*

The maximum number of participants to be recruited locally is 25.

23) Consent Process*

Oncology nurses who work at the University of Miami Sylvester Comprehensive Cancer Center may receive a flyer that will instruct them to reach out to the research coordinator to discuss eligibility. If they meet eligibility criteria and are interested in participating, informed consent will be presented in the first page of the online survey process, participants will electronically sign and enter their name, and click submit to agree to participate in the study. The consent page on the online survey will be available in English.

24) Process to Document Consent in Writing*

All participants recruited will have to enter their full name to electronically sign the consent before starting the online surveys. The password-protected database to which the data is transferred will be at the University of Miami Miller School of Medicine's secure server, REDCap.

References:

Bruine de Bruin, W., Parker, A.M., & Fischhoff, B. (2007). Individual differences in Adult Decision-Making Competence. *Journal of Personality and Social Psychology*, 92, 938-956.

Chochinov H. (2007) Dignity and the essence of medicine: the A, B, C, and D of dignity conserving care. *BMJ* 334: 184-187.

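### The Perceived Stress Scale analysis needs a waitlist group that the design does not describe, and applies a paired t-test to unmatched groups, so it cannot be run as written

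*Combined protocol and SAP*

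**What the plan says.** Section 10 names the endpoint with no comparator: "The secondary outcome will be changes in Perceived Stress Scale from baseline to post-intervention".

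Section 13 then specifies the analysis. Change from baseline to 7-10 weeks is to be compared "between the participants who completed the educational program and participants on the waitlist with a paired t-test". If the two-sided p-value is at most .05, the plan says "our hypothesis that the program results in reduction of perceived stress will be supported". The next sentence extends the approach by analogy to the Self-Efficacy Scale, the Maslach inventory, the two Philadelphia Mindfulness components, the Distress Tolerance Scale and the SF-36.

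The Power Analysis paragraph of the same section describes the testing differently: "We will conduct hypothesis testing to examine differences in our endpoints from pre- to post-intervention". It gives the trial's goal as estimating effect sizes for a larger trial.

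On design, Section 6 says: "The overall study aims to enroll one cohort up to 25 participants in total". Section 22 adds: "The maximum number of participants to be recruited locally is 25". Section 8 sends every enrollee the same baseline link once the target sample is enrolled, and has all nurses complete the same instruments at baseline and after the program. The Section 9 table has one schedule.

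**The concern.** The sentence fails in two ways. It needs a comparison group that the design does not contain. It also names a test that requires each observation in one group to be matched to one in the other, and no matching is described.

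The two possible readings answer different questions. A paired test in one cohort estimates the mean change over time. A comparison with a waitlist estimates the difference in change between trained and untrained nurses. Only the second removes what would have happened anyway, such as seasonal workload, regression to the mean or the effect of repeated questionnaires.

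The p-value rule makes this worse. It uses causal language that presupposes a control group and applies it to a trial that appears to have none. A reader of the results could take an uncontrolled change for a controlled effect. Because the trial exists to supply effect sizes for a larger study, that misreading could pass straight into the next sample-size calculation.

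**Working it through.** **1. Does the design contain a waitlist?**

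| Place | What it implies |
|---|---|
| Section 6 | One cohort, up to 25 in total |
| Section 8, enrollment | All enrollees get the baseline link together; no allocation step |
| Section 8, assessments, and Section 9 | One schedule for all nurses |
| Section 10 | Change from baseline to post-intervention; no comparator |
| Section 13, Power Analysis | Pre- to post-intervention testing; no comparator and no named test |
| Section 22 | Cap of 25 recruited; silent on number of groups |
| Section 13, Perceived Stress Scale sentence | Completers against waitlist |

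Only the last row mentions a waitlist. Nothing describes randomisation, matching or later training for a second group. Some text between Sections 20 (resources) and 21 (confidentiality) was not available for this review and could not be checked.

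**2. Can the named test be applied?** A paired t-test works on within-pair differences. Completers and waitlisted nurses would be different people with no pairing rule. With groups of unequal size, such as 13 and 12, the differences cannot even be formed.

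**3. How much does the choice of reading matter?** The plan gives no power, effect size, SD or allocation ratio, so there is no planned figure to reproduce. Inputs:

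- n = 25, from Section 6; two-sided alpha 0.05, from Section 13.
- Power 80%: my assumption.
- Splits of 13/12 and 10/9: my assumption.
- n = 19: a drop-out of 6/25 = 24%, just inside the 25% limit in Sections 3 and 13.

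Effects are in SDs of the change score. λ is the noncentrality that gives 80% power for a t-test on the stated degrees of freedom.

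One cohort, paired: detectable effect = λ/√n.

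- n = 25 (24 df): 2.920/5 = **0.584**
- n = 19 (18 df): 2.963/4.359 = **0.680**

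Two independent groups: detectable effect = λ × √(1/n₁ + 1/n₂).

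- 13/12 (23 df): 2.926 × 0.4003 = **1.171**
- 10/9 (17 df): 2.973 × 0.4595 = **1.366**

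Ratio at full enrollment: 1.171/0.584 = 2.0.

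95% confidence interval half-width:

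- 25 pairs: 2.064/5 = **0.413 SD**
- 13/12: 2.069 × 0.4003 = **0.828 SD**

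For an assumed effect of 0.5 SD of change, power is 67% with 25 pairs and 22% with a 13/12 split.

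**4. Which analyses are affected?** The Perceived Stress Scale directly. On the natural reading of the sentence that follows, the five further instruments inherit the problem, although that sentence repeats neither the waitlist nor the test. The Cognitive Failures, Mind Wandering and Sunk Cost scales have no stated analysis, so they are outside this point.

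**The case against.** The best defence is that the waitlist wording is a leftover. Remove it and the paired t-test becomes the correct test for one cohort, so there is one error and not two. The Power Analysis and endpoint sentences omit a waitlist without excluding one, and Section 22 gives only a cap. The outcome is secondary, the objective is exploratory and the trial is not powered. The detectable-effect figures compare two designs and do not measure a bias in this one. Finally, moving from completers to everyone assessed goes beyond the waitlist problem.

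Part of this stands. Section 6 and the single schedule in Section 8 carry the contradiction; the other passages are only consistent with it. The figures show what depends on the choice, not an error in results. The factor of two also comes from an unadjusted comparison of change scores. With baseline adjustment, equal variances and an assumed baseline-to-post correlation r, the detectable effect shrinks by about √((1+r)/2). For r = 0.3 this is 1.171 × 0.806 = 0.94, and for r = 0.7 it is 1.171 × 0.922 = 1.08. That is 1.6 to 1.9 times 0.584.

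The core is untouched. The documents nowhere say that the wording is a leftover, and deleting the waitlist alone would leave the causal p-value rule in place. Removing it also leaves open who is analysed, because the sentence then refers only to nurses who completed the program. The analysis set has to be stated in the same edit.

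**Conclusion.** The concern holds and must be fixed. The only test and decision rule stated for the named secondary outcome cannot be executed in the design described, and the named test would not suit two unmatched groups even if a waitlist existed. Depending on the reading, the same 25 nurses can detect 0.58 or 1.17 SD of change (0.68 or 1.37 with 19 assessed), with confidence interval half-widths of 0.41 or 0.83 SD at full enrollment. The two-group figures rest on assumed near-equal splits and an unadjusted analysis. The contradiction itself rests on no assumption beyond the text reviewed. The primary feasibility outcome is unaffected.

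**What to change.** For the single-cohort reading, revise Section 13 as follows.

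1. Delete the waitlist comparison and state: *Within-participant change in the Perceived Stress Scale from baseline to the 7-10 week assessment will be estimated with a 95% confidence interval and tested with a paired t-test in the single cohort.* Use the same wording for the other listed instruments.
2. Define the analysis set as all enrolled participants with both assessments available, whether or not they completed the program, with completers as a supplementary analysis. Section 15 states "Any data collected prior to withdrawal will be destroyed in compliance with IRB procedures", so report how many enrolled participants are missing from the set for that reason.
3. Replace the p-value sentence with: *A significant decrease shows a pre-post reduction, which cannot be attributed to the program without a control group.*

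This is rewording, with no new data and no more participants. The aim in Section 3, which also speaks of the program's effect on stress, should be checked for consistency. The price is a weaker but honest conclusion.

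If a waitlist is really intended, this is a design change. Sections 6, 8 and 9 must describe how the group is formed and when it is trained, and the analysis must be a baseline-adjusted comparison of independent groups. With the same 25 nurses, the detectable effect would then be roughly 1.6 to 2 times as large, under the assumptions above.
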